10.1. Data Set Descriptions

For group 1, after BMS-986156, dose as determined in group 1, an additional 4 patient expansion per dose level (10 patients total for each dose level) will be enrolled in that group, at the determined dose from group 1, to help determine biological endpoints. Should DLTs occur in more than 33% of patients enrolled into this expanded group, dosing at that level will be stopped. The next lower dose level will be considered the safe dose. A review of all DLTs observed will be conducted, and the need to lower the dose will be based on the discussion and agreement between the IRB and the Investigator.

All patients who receive any ipilimumab, BMS-986156, or nivolumab will be considered evaluable for toxicity.

For toxicity and response: all patients receiving at least 1 (concurrent group) or 2 (sequential group) treatment with trial drugs and completed half of the planned radiation treatment (except for group 1 where no radiation is given) will be considered evaluable for toxicity and response and included in the efficacy data set.

Group 1: (Total of 20 patients: 10 patients with 30 mg and 10 patients with 100 mg of BMS-986156, when combined with ipilimumab at 3mg/kg). Nivolumab (480mg) Q4W monotherapy will be administer for 26 cycles.

Group 2: 20 patients: trial drugs, two doses of ipilimumab (3mg/kg) combined with BMS-986156 (dose as determined in group 1) are given before SBRT. SBRT is given sequentially; followed by 2 more doses of ipilimumab + BMS-986156. Nivolumab (480mg) Q4W monotherapy will be administer for 26 cycles.

Group 3: 20 patients: First dose of trial drugs nivolumab (480 mg) and BMS-986156 (30 mg) are given concurrently with SBRT; followed by 3 doses of nivolumab (480 mg) and BMS-986156 (30 mg). Finally, Nivolumab as monotherapy for 22 cycles. Nivolumab will be administered for a total of 26 cycles in this group.

10.1.1. Safety Evaluation

The incidence of clinical and laboratory adverse events will be reported and graded according to the NCI-CTCAE version 4.0 (available at <http://ctep.cancer.gov/reporting/ctc.html>). Adverse events will be reported in frequency tables overall, by intensity, and by relationship. Laboratory values will be reported in shift tables and with summary statistics.

10.1.2. Efficacy Evaluation

Information on the anti-tumor activity of study drug(s) and SBRT combination therapies will be collected throughout this study. Tumor response will be determined using the Immune Related Response Criteria (irRC) as described in section 8.3.

10.2. Analysis

10.2.1. Statistical Analysis

Descriptive statistics will be computed for all relevant outcomes, including tumor response, and biomarker response. Descriptive analysis will include a global assessment of patient outcomes among all three groups. Group analysis will be conducted between groups. All patients receiving at least 1 (concurrent group) or 2 (sequential group) treatment with ipilimumab/Nivolumab/BMS-986156 and completed half of the planned radiation treatment (except for group 1 where no radiation is given) will be considered evaluable for toxicity and response and included in the analysis. Patients receiving any portion of the study drugs or interventions will be evaluable for toxicity.

Demographics, safety, and treatment efficacy will be compared in two separate analyses: (these tests are not for formal hypothesis testing, but for exploratory/descriptive purposes)

1. Among different treatment regimens: treatment group 1 vs. treatment group 2.
2. Among different treatment regimens: treatment group 2 vs. treatment group 3.
3. Among different SBRT targets liver vs lung: treatment group 2 vs. treatment group 3.

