Day 1 and every 21 days: Ipilimumab therapy at 3 mg/kg as a 90 minute intravenous (IV) dose and BMS-986156 (dose as determined in group 1) as a 60 min IV will be given in an outpatient setting. Dose cycles will be repeated every 21 days: on days 1, 22, 43, and 64 for a total of 4 cycles. Nivolumab (480 mg Q4W) will start day 85 and continue every 28 days for 26 cycles. Enrollment of this group will start based on the following criteria. If 2 out of 6 patients, or less, display DLTs, then, enrollment of group 2 can begin. Alternatively, if 3 out of 6 patients, or more, display DLTs, then, enrollment of group 2 cannot begin until 10 patients have been treated in group 1.

SBRT: SBRT will be given after 2 doses of ipilimumab and BMS-986156 on days 29-32 for 50 Gy in 4 fractions or on days 29-40 for 60 Gy in 10 fractions (no SBRT during weekends): SBRT will be directed at 1-4 targetable liver or lung lesion(s). To minimize treatment breaks, patients may start radiation on a Monday.

Group 2

[figure not shown]

Diagram of Treatment Schedule for Ipilimumab + BMS-986156 x 2 → SBRT → Ipilimumab + BMS-986156 x 2 → Nivolumab x 26 (Treatment group 2).

Group 3, 20 patients: Nivolumab + BMS-986156 x 1 + SBRT → Nivolumab + BMS-986156 x 3 → Nivolumab x 22

First dose of Nivolumab + BMS-986156 and SBRT will be given concurrently (early) and followed by Nivolumab + BMS-986156 x 3; then, Nivolumab monotherapy for 22 cycles. Nivolumab will be administered for a total of 26 cycles, either as a combination or monotherapy, in this group. Enrollment of patients for this group will start around the same time as group 1. Choice of treatment group will be at the discretion of PI and treating physician.

Nivolumab therapy at 480 mg dose will be given on day 1 as a 30 minute IV dose and BMS-986156 at 30 mg dose will be given on day 1, 29, 57, 85 as a 60 min IV in an outpatient setting. Nivolumab monotherapy will start on day 113 and will continue for 22 cycles.

SBRT: SBRT will be given on days 1-4 (days 2-5 are acceptable if scheduling does not permit radiation to begin same day as infusions) for 50 Gy in 4 fractions or on days 1-12 for 60 Gy in 10 fractions (no SBRT during weekends). SBRT will be directed at 1-4 targetable liver or lung lesion(s). To minimize treatment breaks, patients may start radiation on a Monday.

Group 3

[figure not shown]

Diagram of Treatment Schedule for Nivolumab + BMS-986156 x 1 + SBRT → Nivolumab + BMS-986156 x 3 → Nivolumab x 22 (Treatment group 3)

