Prior to starting each treatment cycle, patients will arrive at the Clinical Center for Targeted Therapy or Thoracic Medical Oncology Clinic and undergo safety assessments. In all groups, safety will be assessed by physical examination, observation and adverse experiences, and monitoring clinical chemistry and hematology. Disease progression will be based upon the irRC Criteria. All patients will be evaluated for toxicity upon their first receipt of the trial drug(s) and for therapy response after receiving at least 2 doses of drugs and at least half the scheduled radiation doses.

7.1.1 Dose escalation / de-escalation of BMS-986156 when combined with ipilimumab based on a (3+3) design to determine MTD

Ipilimumab (Yervoy™)

Ipilimumab (3 mg/kg) will be administered as a single 90 minute (+/- 15 minutes) intravenous infusion on the first day of each cycle, every 21 days (\pm 3d).

BMS-986156

BMS-986156 (30 mg or 100 mg) will be given as a single 60 min (+/- 15 minutes) intravenous infusion on the first day of each cycle (\pm 3d). When given in combination with Ipilimumab, BMS-986156 will be given every 21 days (\pm 3d).

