10.2.5. Sample Size/Accrual Rate

The maximum planned number of evaluable patients will be 60, with 20 patients being treated in each group (groups: 1, 2 and 3). It is estimated that approximately 3 patients per month will be accrued and an approximate 4 week interval will be allowed between dose levels.

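### The response set requires about four more weeks on treatment in group 2 than in group 3, and section 7.1 states a conflicting rule under which that gap almost disappears

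*Combined protocol and SAP*

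**What the plan says.** Section 10.2.1 limits the response analysis to patients "receiving at least 1 (concurrent group) or 2 (sequential group) treatment with ipilimumab/Nivolumab/BMS-986156 and completed half of the planned radiation treatment", waiving the radiation condition for group 1. Section 10.1 repeats the condition and says that such patients "will be considered evaluable for toxicity and response and included in the efficacy data set". The treatment scheme in section 1 labels group 2 sequential and group 3 concurrent. Both statistical sections also have a wider toxicity set, which takes in anyone given any study drug.

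Section 7.1 has its own rule: patients are evaluated "for therapy response after receiving at least 2 doses of drugs and at least half the scheduled radiation doses". It makes no distinction between groups.

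The schedule is in section 1. For group 2, "Dose cycles will be repeated every 21 days: on days 1, 22, 43, and 64 for a total of 4 cycles"; then "SBRT will be given after 2 doses of ipilimumab and BMS-986156 on days 29-32 for 50 Gy in 4 fractions". The longer group 2 course, with 10 fractions, occupies days 29 to 40. For group 3 the first infusion is on day 1 and the second on day 29, and "SBRT will be given on days 1-4 (days 2-5 are acceptable if scheduling does not permit radiation to begin same day as infusions"; the 10-fraction course runs over days 1-12.

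Section 10.2.5 states: "The maximum planned number of evaluable patients will be 60, with 20 patients being treated in each group". Section 10.2.1 plans comparisons of group 1 with 2 and of group 2 with 3, described as exploratory. Section 10.2.4 plans success probabilities with 95% intervals and states power for response between arms.

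**The concern.** A patient enters the response denominator only by staying on treatment up to a qualifying point, and that point comes at a different time in each SBRT group. Patients with rapid progression, early toxicity or early death are unlikely to respond. Leaving them out raises the observed rate, and the longer the window, the more of them are left out. Group 2's rate and interval would therefore describe patients who got through roughly the first month, while group 3's would describe nearly everyone who started. Part of any group 2 advantage could come from the definition and not from the regimen.

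The two rules also put the same patient in different places. A group 3 patient who stops after one infusion and a full SBRT course is in the set under sections 10.1 and 10.2.1 and out of it under section 7.1.

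**Working it through.** **Qualifying day.** This is the later of the required infusion and the fraction that completes half the course. Fractions are on weekdays from a Monday start, or from the Tuesday for the day 2-5 option. Half of 4 is the 2nd fraction; half of 10 is the 5th. Days are as planned, before the allowed 3-day window.

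| Group and course | Sections 10.1, 10.2.1 | Section 7.1 |
|---|---|---|
| 2, 4 fractions (29-32) | max(22, 30) = 30 | 30 |
| 2, 10 fractions (29-40) | max(22, 33) = 33 | 33 |
| 3, 4 fractions (1-4) | max(1, 2) = 2 | max(29, 2) = 29 |
| 3, 4 fractions (2-5) | max(1, 3) = 3 | 29 |
| 3, 10 fractions (1-12) | max(1, 5) = 5 | 29 |

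For the same course, the gap under 10.1 and 10.2.1 is 30 - 2 = 28, 30 - 3 = 27, or 33 - 5 = 28 days. Under 7.1 it is 30 - 29 = 1 or 33 - 29 = 4 days.

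**Group 1.** The rule gives minimum doses for a concurrent and a sequential group, and section 1 uses those labels only for groups 3 and 2. Section 8.2.2 files group 1 with group 3 under concurrent, but for DLT timing and not for the data set. Group 1's minimum is therefore undefined.

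**The plan's own figure.** With n = 20 per arm and two-sided 10% alpha, power = Φ[(|p1 - p2|√n - 1.645√(2p̄(1 - p̄))) / √(p1(1 - p1) + p2(1 - p2))]. This gives 0.800 (44% v 10%), 0.794 (57% v 20%), 0.794 (68% v 30%) and 0.807 (78% v 40%). The stated 80% is reproduced, for 20 analysed patients per arm.

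**Size of the shift.** Let p be the response rate among all treated patients, d the share of group 2 stopping before qualifying, and s the response rate among those who stop. The evaluable rate is (p - ds)/(1 - d), which is p/(1 - d) when s = 0. The documents give neither d nor s. Assume d = 5-20% in group 2, none in group 3, and s = 0. The 10% and 23% rows use the out-of-field partial response and clinical benefit that section 3.3 reports for the earlier ipilimumab and SBRT trial; 30% is one of the plan's comparator rates.

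| True rate (all treated) | d = 5% | d = 20% | Largest shift |
|---|---|---|---|
| 10% | 0.10/0.95 = 10.5% | 0.10/0.80 = 12.5% | 2.5 points |
| 23% | 0.23/0.95 = 24.2% | 0.23/0.80 = 28.75% | 5.75 points |
| 30% | 0.30/0.95 = 31.6% | 0.30/0.80 = 37.5% | 7.5 points |

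If some who stop do respond, the shift shrinks: with p = 30%, d = 20% and s = 10%, (0.30 - 0.02)/0.80 = 35%. It vanishes at s = p.

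**Effect on the test.** Suppose group 2 is filled to 20 evaluable patients, which the plan does not say. Exact enumeration of the chi-squared test at nominal 10%, with equal all-treated rates, gives a rejection rate that moves from 10.3% to 10.5-11.7% (true 10%) and from 10.5% to 10.6-14.3% (true 30%) over d = 5-20%. If group 2 is not filled, it has 19 to 16 evaluable patients, and the normal-approximation power is 0.784-0.798 at 19 and 0.747-0.765 at 16.

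**The case against.** The strongest reply is that the gap exists under only one of two stated rules. Under section 7.1 it is 1-4 days. That is correct, and it is why the contradiction is part of the point. But 10.1 and 10.2.1 are the sections that define the analysis, so an analyst would most naturally follow them.

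A reader might infer that early failures are removed from one side only. The documents do not support this. Half the planned radiation is required in both SBRT groups, so a group 3 patient who refuses SBRT is left out too, and section 7.3.5 takes SBRT refusers off study in both. The difference is in the length of the window.

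A reader might also infer that excluded patients are replaced. No replacement rule is written. Section 10.2.5 gives a maximum of 60 evaluable patients and, in the same sentence, 20 treated per group. That leaves replacement open.

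Nor does any text say that a group 3 patient who qualifies and then stops counts as a failure. Section 8.3 takes best response from imaging after week 1 of cycle 5 in groups 1 and 2 (from about day 85) or week 2 of cycle 3 in group 3 (from about day 64). A group 3 patient who dies on day 10 is in the set with no qualifying scan. If such patients were set aside as unassessed, early failures would drop out of every group. This weakens any firm statement of the bias, and it exposes a second gap in the plan.

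Progression alone need not remove a group 2 patient, since section 7.3.4 allows treatment to continue at discretion. Finally, the comparison is exploratory and non-randomised, the groups differ in checkpoint drug as well as SBRT timing, and response is secondary. With 20 patients, an exact 95% interval for 2 of 20 is about 1-32%, far wider than the shift. All of this limits the consequences. It does not justify leaving an avoidable bias in group 2's estimate.

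**Conclusion.** The point holds in this form. Under sections 10.1 and 10.2.1, entry to the response set takes about four weeks longer on treatment in group 2 than in group 3; under section 7.1 it does not. Three further matters are unsettled: group 1's minimum doses, how patients without a qualifying scan are counted, and whether non-evaluable patients may be replaced.

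The likely direction is upward for group 2's response and clinical-benefit rates. The size is unknown. It is 0.5 to 7.5 points for true rates of 10-30%, on the assumptions of 5-20% early stopping in group 2, none in group 3, no responses among those who stop, and unscanned but qualifying patients counted as non-responders. The any-drug toxicity set, which serves the primary safety objectives, is not affected. The change is worth making because it costs little, although the affected analyses are secondary.

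**What to change.** - Put one rule in sections 7.1, 10.1 and 10.2.1 for all three groups: the primary set for global response is every patient who received any study drug, which is the existing toxicity set. This also settles group 1.
- State that a patient without a qualifying post-baseline assessment counts as a non-responder.
- Report in-field and out-field irRC for patients who received SBRT, and show per group how many did not. These results remain conditional on reaching SBRT, which comes later in group 2, so they should be read with those counts.
- Keep the present dose-and-radiation set as a labelled sensitivity analysis, with exclusions by group and reason.
- Reword section 10.2.5 so that the 20 per group are treated patients and none are replaced for the response analysis.

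The cost is wording in four sections and one extra table, with no extra patients. Reported response rates will be slightly lower, mainly in group 2.

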2.1. Primary Objectives

- To determine the safe dose of BMS-986156 and Dose Limiting Toxicities (DLT) (30 mg vs 100 mg) when combined with ipilimumab (3mg/kg) for patients with metastatic cancer.
- To evaluate the safety and toxicity profile of ipilimumab (3mg/kg) with BMS-986156 (30 or 100 mg) administered in combination with SBRT targeting 1-4 LIVER lesion(s) for patients with metastatic cancers.
- To evaluate the safety and toxicity profile of ipilimumab (3mg/kg) with BMS-986156 (30 or 100 mg) administered in combination with SBRT targeting 1-4 LUNG lesion(s) for patients with metastatic cancer.
- To determine safety and toxicity profile of Nivolumab (480 mg) with BMS-986156 (30 mg) administered in combination with SBRT targeting 1-4 LIVER lesion(s) for patients with metastatic cancers.
- To determine safety and toxicity profile of Nivolumab (480 mg) with BMS-986156 (30 mg) administered in combination with SBRT targeting 1-4 LUNG lesion(s) for patients with metastatic cancers.

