4.1. Inclusion Criteria

1. Patients must have histological confirmation of solid metastatic cancer (all groups) with at least one metastatic or primary lesion in the liver or lung/chest (groups 2 and 3). All Groups must have measurable disease per irRC criteria.
2. Patients who have completed prior systemic anti-cancer therapies, an interval of 5 drug half-lives or 4-weeks whichever is shorter, is required, prior to enrollment on study. Note: patients with anaplastic thyroid will be waived from this inclusion criteria given the rapid trajectory of their disease.
 - Patients that have previously progressed on immunotherapy such as ipilimumab, anti-PD-1, anti-PDL-1 or talimogene laherparepvec (T-VEC) will be eligible.
3. All patients must have at least one metastatic or primary lesion within the lung/chest or liver located in an anatomical location amenable to SBRT treatment with 50 Gy in 4 fractions or with 60 Gy in 10 fractions, except for group 1.
4. Repeat radiation in fields previously radiated will be allowed at the discretion of the treating physician.
5. Age ≥ 18 years
6. ECOG performance status ≤ 2 (Karnofsky $>60\%$).
7. Patients must have normal organ and marrow function as defined below: (use of growth factors or blood transfusion to achieve these requirements is not allowed 2 weeks prior to study enrollment)
 - Total bilirubin ≤ 2.0 mg/dL. (Does NOT apply to patients with Gilbert's Syndrome)
 - AST(SGOT)/ALT(SGPT) $<2.5 \times$ institutional upper limit of normal.
 - WBC $\geq 2500/\mu\text{L}$, ANC $\geq 1000/\mu\text{L}$
 - Platelets $\geq 75\text{K}$
 - Hemoglobin $\geq 9\text{g/dL}$
 - Creatinine $\leq 2.0 \times \text{ULN}$
8. Patients must be willing and able to review, understand, and provide written consent before starting therapy.
9. Patients with brain metastasis will be included as long as they are free of neurologic symptoms related to metastatic brain lesions and who do not require or receive systemic corticosteroid therapy, $> 10 \text{ mg/day}$ in the 14 days prior to beginning the trial ($\leq 10 \text{ mg steroid}$, e.g.: prednisone, is allowed). We will allow patients with stable brain metastases (clinically and radiographically) for ≥ 4 weeks to enroll on the protocol.

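### Section 10.2.1 defines the liver v lung comparison as group 2 v group 3, which is a regimen comparison; the only planned liver v lung comparison of safety therefore does not compare organs

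*Combined protocol and SAP*

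**What the plan says.** Section 10.2.1 states that demographics, "safety, and treatment efficacy will be compared in two separate analyses", and then lists three. It adds that "these tests are not for formal hypothesis testing, but for exploratory/descriptive purposes". Item 1 is group 1 v group 2. Item 2 is "Among different treatment regimens: treatment group 2 vs. treatment group 3". Item 3 is "Among different SBRT targets liver vs lung: treatment group 2 vs. treatment group 3".

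Elsewhere the plan does not tie groups 2 and 3 to an organ:

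- Section 1 (Treatment Scheme) has the same sentence in the SBRT paragraph of each group: "SBRT will be directed at 1-4 targetable liver or lung lesion(s").
- Section 4.1, item 1, sets one organ requirement for both: "at least one metastatic or primary lesion in the liver or lung/chest (groups 2 and 3").
- Section 2.1 has four SBRT safety objectives, pairing each regimen with each organ. The ipilimumab regimen has a lung objective ("with BMS-986156 (30 or 100 mg) administered in combination with SBRT targeting 1-4 LUNG lesion(s")) and a liver one. The nivolumab regimen has a liver objective ("safety and toxicity profile of Nivolumab (480 mg) with BMS-986156 (30 mg) administered in combination with SBRT targeting 1-4 LIVER lesion(s")) and a lung one.
- Section 10.2.6 leaves the organ to the treating physician when both are amenable to SBRT.

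What does separate the groups, in section 1, is the checkpoint inhibitor (ipilimumab v nivolumab), the timing of SBRT (sequential v concurrent) and possibly the BMS-986156 dose (the dose chosen in group 1 v 30 mg). Assignment follows disease status and clinician discretion; it is not randomised.

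**The concern.** Items 2 and 3 are one contrast with two labels. An analyst who follows the text will report a difference between regimens, plus whatever leaks through from an unequal organ mix, as a difference between liver and lung SBRT.

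For efficacy the loss is partly covered: section 10.2.4 estimates success by target and allows a response model with target as a predictor. For safety it is not covered. Section 10.1.1 tabulates events overall, by intensity and by relationship. Section 10.2.3 compares grade 3 or higher events but names no organ factor. Section 10.2.4 mentions safety comparisons only among the groups. Its by-site comparison for secondary objective d concerns biomarkers (including as predictors of toxicity), not adverse event rates in one organ against the other. Item 3 is therefore the only planned liver v lung comparison of safety, in a trial whose primary objectives are organ-specific safety profiles.

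**Working it through.** **The plan's own figure.** Item 3 has no sample size or power. The only power statement is in section 10.2.4: 20 per arm, chi-squared test, two-sided 10%, 80% power. It reproduces with the pooled-variance formula: 80.0% (44% v 10%), 79.4% (57% v 20%), 79.4% (68% v 30%) and 80.7% (78% v 40%). Nothing below depends on it.

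**What item 3 estimates.** Take one irradiated organ per patient and no regimen-by-organ interaction. Then

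group 2 − group 3 = regimen difference + (liver share in group 2 − liver share in group 3) × (liver rate − lung rate).

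The regimen difference always enters in full. The organ difference enters only in proportion to the imbalance in liver share: 0% at equal shares, 100% only if one group is all liver and the other all lung, and with its sign reversed if the imbalance runs the other way.

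**Inputs for safety.**

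- Liver SBRT, grade 3 or higher toxicity: 2% (section 7.5).
- Lung SBRT: 7.9% (section 7.5; the grade is not stated with the figure, and it is read here as grade 3 or higher).
- Organ difference: 7.9 − 2.0 = 5.9 points.
- Grade 3 treatment-related toxicity on ipilimumab plus SBRT: 34% (section 3.3), without BMS-986156.
- Organ splits and the group 3 rate: not in the documents, so assumed over a range.

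**Case A: only an organ difference exists.** Group rate = liver share × 2% + lung share × 7.9%.

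| Liver patients of 20, group 2 v group 3 | Group 2 | Group 3 | Item 3 shows (of 5.9 points) |
|---|---|---|---|
| 10 v 10 | 4.95% | 4.95% | 0 |
| 12 v 8 | 4.36% | 5.54% | 1.2 |
| 15 v 5 | 3.475% | 6.425% | 3.0 |
| 20 v 0 | 2.0% | 7.9% | 5.9 |

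**Case B: only a regimen difference exists.** The true organ difference is 0 and group 2 has 34%. Power is by exact enumeration, 20 v 20, two-sided 10%.

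| Group 3 rate (assumed) | Item 3 shows, labelled liver v lung | Significant, uncorrected chi-squared | Significant, Fisher |
|---|---|---|---|
| 10% | 34 − 10 = 24 points | 60% | 45% |
| 20% | 34 − 20 = 14 points | 27% | 17% |
| 34% | 0 points | 10% | 5% |

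**Case C: both.** With 34% v 10% by regimen and liver counts running from 15 v 5 to 5 v 15, item 3 ranges from 24 − 2.95 = 21.05 to 24 + 2.95 = 26.95 points. The regimen effect dominates whatever the split.

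**Precision of a correct organ contrast.** With 20 liver and 20 lung patients, the 95% half-width is 1.96 × √(0.02 × 0.98/20 + 0.079 × 0.921/20) = 1.96 × 0.068 = 0.133, or about ±13 points. Expected events are 20 × 0.02 = 0.4 and 20 × 0.079 = 1.6. At these rates exact power at two-sided 10% is 14% (uncorrected chi-squared) or 1% (Fisher). The corrected comparison can only be descriptive.

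**The case against.** Five points can be made for the plan.

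1. *Item 3 may mean group 2 v group 3 within each organ.* That would differ from item 2 and would suit the by-organ, by-regimen objectives in section 2.1. But the item says liver v lung, and items 1 and 2 use the same form to name what is being contrasted. The text does not support this reading, though a table of organ by group would serve it too.

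2. *The groups may have been thought of as organ-linked.* Section 1 says that patients with both liver and lung lesions are assigned by provider preference, and section 7.1 treats such patients as meeting criteria for more than one group. If group 2 were all liver and group 3 all lung, item 3 would carry the full 5.9 points. But no current group definition is organ-specific, the objectives rule it out, and the regimen difference would still be mixed in.

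3. *No objective requires an organ contrast, and the tests are exploratory.* Both are true. Section 2.1 asks for profiles, and adverse events can still be described by organ. This limits the consequence; it does not make item 3 correct.

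4. *The duplication would be noticed.* Perhaps, since items 2 and 3 would return the same result. The analyst would then have to decide after seeing the data what item 3 was meant to be.

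5. *The correction recovers little inferential information.* This stands: with about two expected events in 40 patients, the gain is a correctly labelled description, not a test.

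**Conclusion.** The point holds. Item 3 of section 10.2.1 is a group 2 v group 3 regimen comparison labelled liver v lung, and the one planned organ comparison of safety would not be made if the text were followed. That conclusion comes from the text alone.

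The sizes are illustrations: between none and about half of a 5.9-point organ difference would show at splits from 10 v 10 to 15 v 5, and 0 to 24 points of pure regimen difference could appear under the organ label. They rest on assumed organ splits, an assumed group 3 rate of 10% to 34%, the reading of 7.9% as grade 3 or higher, one organ per patient and no regimen-by-organ interaction. No dose decision, stopping rule or sample size is affected. The probable intent is liver v lung among irradiated patients, because section 10.2.4 treats group and site as separate factors, but the plan does not say so. It should be corrected before analysis.

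**What to change.** Rewrite item 3 as: patients given liver SBRT v patients given lung SBRT, within groups 2 and 3, stratified by treatment group or shown separately within each group, for safety as well as efficacy, descriptive only. Showing the organ-by-group table also delivers the four SBRT safety profiles in section 2.1. State how a patient irradiated in both organs is classified in this analysis, or state that section 10.2.6 means one organ per patient. Change the announced number of analyses from two to three.

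The cost is a short text edit. No new data are needed, since SBRT planning records the irradiated organ, and sample size is unchanged.
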